8.3 Clinical Laboratory Tests

Summary statistics for chemistry, hematology, and urinalysis laboratory tests will be presented at baseline, and for each visit. Laboratory tests results and changes from baseline to each visit will be summarized using descriptive statistics. For the STP 2279-002 subjects, changes will be calculated from the last non-missing value prior to the first dose of Revcovi in the STP 2279-002 Study.

Listings for laboratory data will be presented identifying clinically significant abnormal results and out-of-normal range values. Clinically significant abnormal results and results out of normal range will be identified by the status: Abnormal, NCS will be classified as 'Out of normal range result'; Abnormal, CS will be classified as 'Clinically significant abnormal results'; and normal status and missing status will be classified as normal result.

Results of pregnancy tests will be listed, but not summarized. The values of positive tests in the urine analysis will also be listed but not summarized.

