percentage by body system, preferred term, and treatment groups

as naïve patients or patients transitioning from Adagen. In

Study Drug: Revcovi (elapegademase-lvlr)	IND No.: 100,687			
Protocol No.: Development	Indication:			
CLI-06814AA1- 01	ADA-deficient severe combined immunodeficiency			
Protocol Title: Single Arm, Open-Label, Multicenter, Registry Study of Revcovi (elapegademase-lvlr) Treatment in ADASCID Subjects Requiring Enzyme Replacement Therapy				
 addition, AEs will be summarized by relationship to Revcovi and by severity. All SAEs will also be summarized in a frequency table. Safety laboratory parameters (chemistry, hematology, and urinalysis) will be summarized descriptively at each time point; out-of-range values will be listed. Vital sign parameters will be summarized descriptively at each time point. 				
 Clinical Status: These endpoints will be summarized descriptively: Incidence of infection Incidence and duration of hospitalizations Growth: Height-for-age and weight-for-age Z-scores Survival: Descriptive summary of subject status. 				
Quality of Life Analysis: Quality of Life : QOL will be assessed for subjects up to and including those who are 18 years old using the age-specific Pediatric Quality of Life Inventory (PedsQL). Subjects over 18 years old will be assessed using the SF-36 and Primary Antibody Deficiency Quality of Life Questionnaire (PADQOL). Data will be summarized by age and stratified by previous participation in the Phase III study STP-2279-002. Subjects that age out of PedsQL and into PADQOL will be summarized only in the PedsQL while their PADQOL will be listed.				

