13.2.3.5 Safety Data Analysis

Safety summaries will be presented by whether or not they previously participated in study STP-2279-002.

Adverse Events and Serious Adverse Events – AEs will be categorized using Medical Dictionary for Regulatory Activities (MedDRA) Version 22.1 or later. Summaries will be presented for all treatment-emergent AEs, AEs determined by the Investigator to be treatment-related, serious adverse events (SAEs), AEs causing withdrawal from study, AEs causing discontinuation of Revcovi, and non-serious AEs. The intensity of toxicities will be graded by the Investigator as mild, moderate, or severe as described in Section 12.2.5. In addition to being summarized as AEs, infectious complications and hospitalizations are considered efficacy measures as described in Section 10.8.

AE incidence will be calculated based on the number of subjects per AE category. For each subject who has multiple AEs classified to the same category, that subject will be tabulated under the maximum toxicity intensity for that AE category. The incidence of AEs will be tabulated by MedDRA system organ class and preferred term.

An AE onset between the date of the first dose of Revcovi and 30 days after the last dose of Revcovi is considered as a treatment-emergent AE.

Laboratory Safety Data – Hematology, chemistry, and urinalysis data will be summarized by timepoint of collection and by treatment group. In addition, listings for laboratory data will be presented identifying clinically significant abnormal results and out-of-normal range values will be listed.

Other Safety Data – The results of antibodies against Revcovi and antibodies against PEG will be summarized. The relationships between immunogenicity, biochemical endpoints, and the clinical toxicities will be examined as appropriate. Concomitant medications and findings in physical examinations will be listed and described textually as recorded in the CRF. Descriptive statistics of vital signs measurements as well as changes from baseline will be tabulated; abnormal vital sign values will be reported and summarized as AEs.

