14.8.1 Regulatory Documentation

Prior to initiating the study, the Investigator provides the CRO or Chiesi the following documents:

- A signed Form FDA 1572 or equivalent
- A current curriculum vitae for the Investigator and each sub-Investigator listed on the Form FDA 1572
- Copy of the current medical licenses for the Investigator and Sub-Investigators, as applicable
- Written IRB/IEC approval of the protocol, informed consent form and any other material provided to potential study participants with information about the study (e.g., advertisements)
- A copy of the IRB/IEC-approved informed consent document and HIPAA/privacy authorization

- Current IRB/IEC membership list for the reviewing IRB/IEC and/or multiple project assurance number or an IRB organization number under the Federal Wide Assurance program
- A signed Investigator Protocol Agreement (Section 15 of study protocol)
- Completed financial disclosure form for the Investigator and all Sub-Investigators
- Local reference laboratory documentation, including current laboratory certification, current laboratory normal values, and director's CV

During the course of the study, the Investigator maintains current records to document regulatory compliance with the study including: the study protocol and amendments, all versions of the PI in effect during study conduct, signed Investigator Agreement protocol page(s), Form FDA 1572 or equivalent , curricula vitae of the Investigator and sub-Investigators, medical licenses of the Investigator and sub-Investigators, financial disclosure of the Investigator and sub-Investigators, IRB/IEC approvals of the protocol, protocol amendment(s), informed consent form(s), IRB/IEC membership list, IRB/IEC approved informed consent form(s), IRB/IEC correspondence, protocol deviations, study logs (as provided by Chiesi), drug dispensing and accountability records, safety reports, and all correspondence pertaining to the conduct of the study. Regulatory documentation is reviewed by Chiesi during monitoring visits to assure regulatory compliance.

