TM 102	3103	3058-3148
TM 105	3194	3149-3240
TM 108	3286	3241 or later
1-month post-	30	1-60
transplantation*		

6-month post-	182	61 onwards
transplanation*		

*Reference date for the 1- and 6-month post-transplantation visit is the date of the last dose of REVCOVI

Suggested Visit	Targeted Study day	Visit window
Enrollment/Baseline	Last available data	-∞ - 1
	prior or at Study Day 1	
TW 2	15	1-22
TW 4	30	23-37
TW 6	45	38-52
TW 8	60	53-67
TW 10	75	68-83
TW 12	91	84-106
TM 4	121	107-136
TM 5	151	137-166
TM 6	182	167-197
TM 7	212	198-227
TM 8	242	228-257
TM 9	273	258-319
TM 12	365	320-410
TM 15	456	411-501
TM 18	547	502-592
TM 21	638	593-684
TM 24	730	685-776
TM 27	822	777-867
TM 30	913	868-958
TM 33	1004	959-1049
TM 36	1095	1050-1141
TM 39	1187	1142-1232
TM 42	1278	1233-1324
TM 45	1370	1325-1415
TM 48	1461	1416-1506
TM 51	1552	1507-1597
TM 54	1643	1598-1689
TM 57	1735	1690-1780
TM 60	1826	1781-1871
TM 63	1917	1872-1962
TM 66	2008	1963-2055

Adagen-Naïve Subjects

6-month post- transplanation*	182	61onwards
1-month post- transplantation*	30	1-60
TM 108	3286	3241 or later
TM 105	3194	3149-3240
TM 102	3103	3058-3148
TM 99	3012	2967-3057
TM 96	2921	2876-2966
TM 93	2830	2785-2875
TM 90	2739	2694 or later
TM 87	2647	2602-2693
TM 84	2556	2511-2601
TM 81	2465	2420-2510
TM 78	2374	2329-2419
TM 75	2282	2237-2328
TM 72	2191	2146-2236
TM 69	2100	2056-2145

*Reference date for the 1- and 6-month post-transplantation visit is the date of the last dose of REVCOVI

For by-visit summaries, if there are multiple assessments in the specified time windows, the value most closely to the targeted time point will be used for the analysis. If 2 timepoints have the same distance from the targeted time point, the value after the targeted timepoint will be used for the analysis.

Missing data will not be imputed.

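### SAP 8.3 classifies a laboratory result with a missing status as normal, so abnormal values with a blank status go unidentified in the safety laboratory listings

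*SAP*

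**What the plan says.** SAP 8.3 (Clinical Laboratory Tests) plans descriptive statistics by visit for chemistry, haematology and urinalysis. For individual results it says: "Listings for laboratory data will be presented identifying clinically significant abnormal results and out-of-normal range values". The method follows: "Clinically significant abnormal results and results out of normal range will be identified by the status". A status of abnormal but not clinically significant becomes an out-of-range result, and a status of abnormal and clinically significant becomes a clinically significant result. For everything else, "normal status and missing status will be classified as normal result". SAP 8.3 does not compare the value with a reference range, and it keeps no category for an unknown status.

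The protocol states the requirement twice. The synopsis says "out-of-range values will be listed". Protocol 13.2.3.5 says "listings for laboratory data will be presented identifying clinically significant abnormal results and out-of-normal range values will be listed". Neither place makes the listing depend on a site having completed a status field. SAP 8.1 declares no change to the safety analysis planned in the protocol.

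**The concern.** Whether a value is out of range depends on the value and its reference range. Whether the status field was filled in is a matter of data entry. The rule treats a gap in data entry as evidence of normality, and it can move an abnormal result only into the normal class.

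This matters because the status is the only planned means of identifying individual abnormal laboratory results. SAP 8.3 has no shift table and no count of out-of-range results that would reveal a value missed in the listing. Protocol 5.4 describes the study as a post-marketing commitment, and its report would class results as normal with nothing recorded to support that.

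Blank statuses are plausible, though not documented. Safety laboratory tests are optional and done locally (Protocol 10.5.3). Sites enter them from standard-of-care records (Protocol 14.7.1), and retrospectively for subjects already on Revcovi at enrolment (Protocol 7.1).

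**Working it through.** The plan gives no figure to reproduce. The check sets the rule beside the protocol's requirement and then works out the direction and form of the error.

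**Step 1: the rule against the requirement, for a value that is truly out of range.**

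| Recorded status | Class under SAP 8.3 | Identified as the protocol requires? |
|---|---|---|
| Abnormal, clinically significant | Clinically significant abnormal | Yes |
| Abnormal, not clinically significant | Out of range | Yes |
| Missing | Normal | No |

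Only the third row fails. Nothing elsewhere in the SAP or protocol overrides it.

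**Step 2: the rule against the SAP's other rules for missing safety fields.** A missing adverse event severity keeps its own category when no graded severity exists (SAP 8.2). A missing relationship is taken as related (SAP 8.2 and 13.5). A missing seriousness flag, however, is counted as non-serious (SAP 8.2), so the SAP is not uniformly cautious. SAP 13.3 also says "Missing data will not be imputed". That sentence closes the section on visit windows, so it is weak evidence of a contradiction and the point does not rest on it.

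**Step 3: form of the error.** Let N be the number of results, p the share truly abnormal, and m the share of those abnormal results with a blank status.

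- Abnormal results classified as normal: N × p × m
- Share of all results identified as abnormal: p × (1 − m)
- Share of abnormal results missed: m
- Normal results classified as abnormal because of the rule: 0

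**Step 4: illustration.** The documents give neither p nor m, so these are assumptions: N = 1,000 and p = 20%, which gives 200 abnormal results.

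| Assumed m | Abnormal classified as normal | Share identified as abnormal |
|---|---|---|
| 5% | 200 × 0.05 = 10 | 20% × 0.95 = 19% |
| 10% | 200 × 0.10 = 20 | 20% × 0.90 = 18% |
| 30% | 200 × 0.30 = 60 | 20% × 0.70 = 14% |

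The share missed simply equals the assumed m. The table shows the form of the error and does not estimate it.

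**Step 5: what the rule does not touch.** SAP 8 says that all safety data are listed, so the number itself remains visible. The by-visit statistics use the numeric values and include the minimum and maximum (SAP 5). ADA activity and dAXP are judged against numeric thresholds (SAP 7.2.1), and lymphocyte subsets and immunoglobulins are summarised numerically (SAP 7.2.2). None of these uses the status.

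**The case against.** The strongest reply is that little depends on the rule. It governs identification in listings of tests the protocol does not require. No planned estimate, rate or summary table changes, and the value can still be read in the listing. Laboratory abnormalities judged clinically meaningful reach the adverse event data separately (Protocol 10.5.3, SAP 8.2), and a monitoring committee reviews safety data at least yearly (Protocol 7.7). Edit checks and manual queries exist (Protocol 14.7.1), the investigator is responsible for completeness of the eCRF (Protocol 14.8.3), and Protocol 13.2.4 leaves the handling of missing data to the SAP.

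Most of this stands, and it limits the severity. It does not remove the point:

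- The adverse event route starts only with treatment and covers only what the investigator judges meaningful. Out-of-range values not judged significant, and baseline values, have no second route.
- The minimum and maximum help only if the value is the one selected for its visit window; SAP 13.3 keeps the value closest to the target day.
- The query examples in Protocol 14.7.1 do not name a missing laboratory status. The list may not be exhaustive, so this shows neither that blanks are caught nor that they are missed.
- Leaving missing data to the SAP does not make it sound to treat an unknown status as normal.

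A reader might infer three stronger things that the documents do not support. The first is that abnormal values vanish from the report: they are misclassified, but the numbers remain listed. The second is that a particular share of abnormal results, such as 10% to 30%, is affected: no rate of missing status is given. The third is that out-of-range status can readily be derived because sites must supply "current laboratory certification, current laboratory normal values". That item in Protocol 14.8.1 belongs to the regulatory file collected before the study starts. It does not show that a range is stored with each result, or that the ranges cover retrospective results.

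**Conclusion.** The point holds as a should-fix. As written, SAP 8.3 classifies any abnormal chemistry, haematology or urinalysis result with a blank status as normal, so the listings do not identify it. This conflicts with the protocol's statement that "out-of-normal range values will be listed", and SAP 8.1 declares no change. The error is one-directional. It equals the share of abnormal results with a blank status, which the documents do not give; it could be nil if statuses are complete.

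It is not a must-fix, because the numeric values stay listed, the by-visit summaries are unaffected, and clinically meaningful abnormalities after treatment start should also appear as adverse events. One caveat on the comparison: the SAP says it is based on protocol Version 4.0, while the protocol text available is marked Version 5.0, so the conflict shown is with the current protocol.

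**What to change.** 1. Replace the rule in SAP 8.3 so that a missing status is its own category, such as 'status not available', and is never pooled with normal. Report the number of results in that category.
2. Query blank laboratory statuses before database lock.
3. Where a reference range for the result is held in the database, also flag low or high from the numeric value, with value and range in the same units (SAP Appendix C sets the reporting units). A range cannot supply clinical significance, so an unflagged clinically significant result can be recovered only through the query.

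Item 1 needs no new data: a sentence of SAP text, one derived category and a count. Item 2 adds some queries for the sites. Item 3 depends on what the database holds and should not delay the other two. The downside is slightly longer listings and a few more queries.

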8.4 Vital Signs

Summary statistics for vital signs will be presented for all suggested visits. Vital signs results and changes from baseline to each visit will be summarized using descriptive statistics. For the STP 2279-002 subjects, changes from baseline will be handled in the same way as for the laboratory values.

Listings for vital signs will be provided.

8.5 Physical Examination

Physical examination findings will be reported as medical history or adverse events and analyzed as such.

8.6 **Procedures**

Procedures performed after the first dose of Revcovi will be listed but not summarized.

8.7 Study Drug Administration

Study drug administration for Revcovi will be summarized by subject status based on the prescribing data for Adagen/Revcovi Treatment. For subjects transitioning from the STP-2279-002 study, study drug administration will be summarized from the first dose of Revcovi in the CLI-06814AA1-01 study until the end of the CLI-06814AA1-01 registry.

Duration of treatment (months treated) is the number of days on treatment based on the first and last days of treatment with the study drug (last day of study drug – first day of study drug + 1)/30.4375. For subjects who are still taking Revcovi at the end of the observational period,

the duration will be counted until the date of study completion or study discontinuation, respectively, as reported on the study disposition page. Duration of treatment will be summarized by descriptive statistics.

The number of doses administered will be summarized by descriptive statistics. The number of doses will be calculated by the number of weeks x number of times per week for each treatment period and summed for each subject.

Frequency statistics will be calculated for the number of subjects with dose modifications and for subjects with dose omissions/delays will be calculated. A dose omission/delay will be defined as a dose interruption of 8 days or more. The duration of the dose interruption will be calculated as start of the subsequent treatment period – end date of the previous treatment period + 1 day. The duration of dose interruptions will be summarized on subject level, i.e. multiple dose interruptions will be summed on subject level and summarized by descriptive statistics. Duration of dose interruptions will be calculated as an absolute value and as percentages of the duration of treatment.

The total weekly dose of Revcovi (in mg/kg) will be summarized for each suggested visit. This is defined as the dose on the targeted study day. If a new dose is started on the targeted study day, the new dose is used as weekly dose. The weekly dose is calculated as dose per administration (mg) x number of times per week.

Prescribing data of Revcovi will also be presented in a data listing. Revcovi administration data from the subject diary will be listed but not summarized.

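### SAP 8.7: the weekly dose labelled mg/kg has a formula with no weight divisor, and the interruption formula does not match the section's own inclusive day count

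*SAP*

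**What the plan says.** **Dose.** SAP 8.7 states: "The total weekly dose of Revcovi (in mg/kg) will be summarized for each suggested visit". The formula follows two sentences later: "The weekly dose is calculated as dose per administration (mg) x number of times per week". The section names no body weight. SAP 6.7, by contrast, does ask for the prior Adagen dose per kg, although it too does not say which weight. Protocol 10.10.1 expresses the starting dose of Adagen-naïve subjects per ideal body weight. Protocol 10.5.1 has measured weight in kg recorded at the physical examination.

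**Interruptions.** SAP 8.7 computes months on treatment as ("last day of study drug – first day of study drug + 1)/30.4375", so the first and last day both count as treated. An interruption is "start of the subsequent treatment period – end date of the previous treatment period + 1 day". The threshold is: "A dose omission/delay will be defined as a dose interruption of 8 days or more". Per subject, "multiple dose interruptions will be summed on subject level and summarized by descriptive statistics", and: "Duration of dose interruptions will be calculated as an absolute value and as percentages of the duration of treatment".

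Neither document says whether the end date of a treatment period is the last treated day or the first day off drug. SAP 8.7 does not say whether gaps below the threshold enter the per-subject sum. SAP 14 replaces a missing day in a Revcovi start or stop date by the first of the month.

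**The concern.** The dose label and the dose formula have different units, so the table cannot be programmed uniquely from the text. A programmer who sees the mismatch still has to choose the weight. The choice matters because Protocol 6.2 makes dose adjustment part of the objective, and Protocol 6.3 lists weight gain among the explanations for a fall in ADA activity. A per-kg dose based on an unstated weight cannot show reliably whether dosing kept pace with growth.

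The interruption formula adds a day where the section's own convention requires one to be subtracted. This changes a duration, a percentage of treatment time, and the number of subjects reported with an omission or delay. Protocol 13.2.3.3 commits to describing delays and omissions. The tables in SAP 8.7 are their only summary, since diary data appear only in listings.

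**Working it through.** The plan gives no worked figure to reproduce, so the check is of units and day counts.

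**1. Units of the weekly dose**

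- Formula as written: mg per administration × administrations per week = mg per week.
- Quantity named in the label: mg per week ÷ body weight in kg.

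Example: 0.4 mg/kg per week (Protocol 10.10.1, Adagen-naïve start) at an assumed 4 kg is 0.4 × 4 = 1.6 mg per week. The formula prints 1.6 where 0.40 is meant. If the 1.6 mg per week stays constant, the per-kg value depends on the weight used (all weights assumed):

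| Weight used | mg/kg per week |
|---|---|
| 4 kg | 1.6/4 = 0.40 |
| 6 kg | 1.6/6 = 0.267 |
| 8 kg | 1.6/8 = 0.20 |
| 10 kg | 1.6/10 = 0.16 |

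A baseline weight of 4 kg and a current weight of 10 kg would give values that differ by a factor of 0.40/0.16 = 2.5 for the same injections.

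**2. Interruption length**

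Let E be the end of one period and S the start of the next. The SAP value is S − E + 1.

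- E is the last treated day: untreated days = S − E − 1, so the excess is 2.
- E is the first day off drug: untreated days = S − E, so the excess is 1.

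Additivity check, with treated periods on days 1–100 and 111–365:

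- Treated days: 100 + (365 − 111 + 1) = 100 + 255 = 355.
- Untreated days: 111 − 100 − 1 = 10, and 355 + 10 = 365.
- SAP interruption: 111 − 100 + 1 = 12, and 355 + 12 = 367, which is 2 more than the 365 days available.
- As a share of 365 days: 12/365 = 3.29% instead of 10/365 = 2.74%.

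If the end date were instead recorded as day 101, the first day off, the SAP value is 111 − 101 + 1 = 11 for the same 10 untreated days.

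**3. Effect on the 8-day rule**

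| Untreated days | SAP value, E = last treated day | SAP value, E = first day off |
|---|---|---|
| 5 | 7 | 6 |
| 6 | 8, flagged | 7 |
| 7 | 9, flagged | 8, flagged |
| 8 | 10, flagged | 9, flagged |

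If the threshold is meant in untreated days, gaps of 6 and 7 days (first reading) or of 7 days (second reading) are flagged although they fall short of it.

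**4. Imputed dates**

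By SAP 14, a missing stop day set to the first of the month moves E earlier and lengthens the gap. A missing start day set to the first moves S earlier and shortens it. The direction therefore depends on which date is incomplete.

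**The case against.** **The unit is stated.** The label fixes the output as mg/kg, and the formula can be read as only the step from single dose to weekly dose. A printed value far from the protocol's 0.2 and 0.4 mg/kg would be noticed. This stands in part: mg/kg is evidently intended. It does not supply the weight.

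**The formula may be an inclusive span.** Later date minus earlier date plus 1 is the SAP's usual count. Read as the span from E to S with both days included, it has no excess. But both days are already counted as treated in the duration, and the SAP nowhere says an interruption includes them. On this reading two dates 7 days apart give 7 + 1 = 8 and meet the rule. That does not show that on-time weekly injections will be flagged, because SAP 8.7 works from prescribing data and period dates need not be injection dates. Nor does the SAP say that the 8 days are untreated days. What stands is that the dates and the threshold must be defined before any exact error can be asserted.

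**Stronger readings a reader might infer.**

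- That the missing divisor will reverse the order of infant and adult dosing. The SAP groups subjects by Adagen history and STP-2279-002 participation, not by age, and Protocol 10.10.1 lets doses vary within those groups.
- That dose changes without a gap will accumulate as interruption days. This needs the unstated assumption that short gaps are summed; SAP 8.7 counts dose modifications separately.
- That date imputation always inflates gaps. It can also shorten them.
- That the count of doses conceals missed injections. SAP 8.7 states openly that the count is derived from weeks and frequency, using prescribing data.

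**Conclusion.** Two points hold. First, the weekly dose formula lacks the divisor that its label requires, and the weight is unspecified in both date and type. Second, the interruption formula is inconsistent with the inclusive duration count beside it: untreated days are overstated by 2 or by 1 per interruption, depending on what the end date means. The percentage of treatment time therefore combines two counting rules, and the 8-day rule cannot be tied to a definite day count.

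The 2.5-fold spread in the dose example rests on assumed weights. The day excess rests on the two readings of the end date and on an interruption meaning untreated days. The documents do not give the number of period boundaries or incomplete dates, so the effect on the final tables cannot be estimated. It is confined to descriptive exposure summaries. The change should be made, but nothing inferential depends on it, and it implies no view on dosing.

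**What to change.** In SAP 8.7:

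- Divide the weekly dose by body weight in kg and name the weight, for example the last recorded weight on or before the targeted study day. Footnote that Adagen-naïve starting doses are expressed per ideal body weight, so the tabulated value may differ from the prescribed one.
- Define the start and end dates of a treatment period.
- If end dates are treated days, compute an interruption as S − E − 1, with 0 for a same-day change.
- State the 8-day analysis threshold on that same quantity, and say which gaps enter the per-subject sum.
- Flag any gap derived from an imputed start or stop day.

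The cost is SAP wording and programming. Weight is already collected under Protocol 10.5.1, so no new assessment is needed. Because Protocol 11.2 makes the schedule a suggestion and SAP 5 reports that actual timing departs from it, the last weight may be old in a growing infant; listing its date beside the dose would show this.
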